**C. Study Design Overview:** A stratified cluster randomized design will be used. Using a 1:1 ratio, we randomly assigned 136 nursing homes (with approximately 16,700 residents) to: 1) AHRQ-funded COVID-19 ECHO that includes 16 weekly telehealth sessions addressing COVID-19 guidelines and best practices plus 9 weekly optional 60-minute office hour sessions or 2) AHRQ-funded COVID-19 ECHO plus 17 sessions with a focus on stakeholder identified needs and CDC infection control training. Randomization was stratified by geographic location (rural vs. urban), current COVID-19 infection rate (some vs. none), and facility capacity (<60 beds vs. ≥60 beds). Patient-centered outcomes (nursing home residents with COVID-19 infections, flu-like illness, hospitalizations, deaths, and QOL) will be assessed at baseline (intervention start date), 4, 6, 12, and 18 months. Our study is guided by the RE-AIM framework to critically evaluate both effectiveness and implementation outcomes of the proposed intervention. The RE-AIM framework is frequently utilized to improve sustainable adoption and implementation of effective, generalizable, evidence-based interventions

PRINCIPAL INVESTIGATOR (LAST, FIRST, MIDDLE): [name]

like Project ECHO. A formal study protocol will be developed upon funding (RQ-2). This protocol will further outline a data management plan that addresses data collection, organization, handling, description, preservation and sharing (IR-7).

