
PRINCIPAL INVESTIGATOR (LAST, FIRST, MIDDLE): [name]

as well as barriers and facilitators (i.e., inner and outer contexts, Organizational Readiness for Implementing Change scale [ORIC], Practice Adaptive Reserve scale [PAR], Change Process Capacity Questionnaire [CPCQ]).

Table 4. Proposed Study Outcomes

Study Outcomes	Description	Data Source (Timing of Assessment)
Reach	Absolute number, proportion, and representativeness of nursing homes and staff who agree to participate	Study recruitment logs and staff survey (baseline)
Effectiveness	Primary outcome: COVID-19 infection rate reduction; Secondary outcomes: flu-like illness, hospitalizations, deaths, QOL	National COVID-19 Nursing Home data file and CMS Minimum Data Set (baseline, 4, 6, 12, 18 months)
Adoption	Absolute number, proportion, and representativeness of nursing homes and staff who initiate and complete the ECHO series; and barriers and facilitators for adoption	Study participation logs; staff survey (baseline, 6 months) with validated measures including ORIC, PAR, and CPCQ; and key informant interviews (6 months post intervention)
Implementation	Nursing home staff knowledge and attitudes towards the various intervention functions and components, their level of implementation, and barriers and facilitators for implementation	Selected items from CDC's Preparedness Checklist; staff surveys (baseline, 6, 12 months) with validated measures; and key informant interview (6 months)
Maintenance	Extent to which implemented guidelines for emergency preparedness in an infectious disease outbreak become part of nursing home policies post-intervention	Key informant interview (12 months)

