Q8. What is your facility doing to increase vaccine confidence and uptake among staff?

[figure not shown]
**Sample Size, Power, and Analytic Plan (IR-1):** The proposed study is a cluster randomization trial (stratified; RC-5). The intervention will be given at the cluster level (nursing homes). Study objectives and primary outcomes will be considered at both the cluster and individual levels (RC-1). There are several reasons why a cluster randomization was preferred over a traditional randomized controlled trial. First, the cluster randomization was preferred because the target of the intervention is a collective (i.e., a nursing home) rather than a particular patient. Second, cluster randomization was preferred due to potential contamination. Third, cluster randomization is compelling for practical reasons, when patient-specific level protocols would be nearly impossible like in the nursing home care (RC-2). The potential confounders will be balanced out by the randomization design. We will compare the observed confounders between two study arms and adjust them in the analysis if they are not balanced by design. Further, we will measure potential confounders before the start of exposure and report data on potential confounders with study results (CI-1; CI-4). We will monitor data collection for the RE-AIM metrics (surveys and interviews), routinely checking and following up with study sites to recover missing data (MD-1). We will use multilevel models such as mixed effects models or marginal models based on generalized estimating equation (GEE) method to estimate the intervention effect". Both methods are valid if the outcome data are missing completely at random. For data missing at random (i.e., depends on observed data only), mixed models can still provide valid inference and the weighted GEE methods will be considered to account for this type of missing data. We will also conduct sensitivity analyses to examine the robustness of results to missing data. Multiple imputation methods will be used to address the missing data in the covariates (MD-2, MD-4). Further, we plan to record and report all reasons for dropout and missing data and account for patients. Specifically, we will record reasons for missing data and perform analysis based on intention-to-treat principle as described below (MD-3). We have 126 nursing homes (62 in ECHO and 64 in ECHO plus) continuing to the phase 2 of the study. According to the CMS weekly data as of April 2021, the average weekly COVID-19 infection rate was 0.1%, average number of residents in nursing homes (cluster size) was around 75-80 and the coefficient of variation of cluster size was at about 0.76. Assuming 1% infection rate in the ECHO arm over the 9 weeks when additional topic sessions are provided in the ECHO plus arm, our study will have 80% power to detect a significant intervention effect if the infection rate is reduced to below 0.3% in ECHO plus arm. This calculation was based on a two-sided statistical test of difference between Poisson rates at alpha=0.05 and intracluster correlation coefficient (ICC)  $\leq 0.01$ . Our power will be below 80% if ICC is 0.05 or higher even if the infection rate is nearly zero in the ECHO plus arm. We will test the effectiveness of ECHO plus group by performing both individual-level analyses (primary) and cluster-level analyses (secondary) following the intention-to-treat principle. To account for intracluster correlations within nursing homes, we will use multilevel models such as mixed effects models or marginal models based on generalized estimating equation (GEE) method to estimate the intervention effect. The outcomes after 6-months of intervention will be analyzed using generalized linear models, with an appropriate link function depending on outcome type. Intervention effect on infection risk will be estimated as odds ratio or incidence

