
PRINCIPAL INVESTIGATOR (LAST, FIRST, MIDDLE): [name]

rate ratio based on logistic, Poisson or negative binomial regressions. State and cohort variations will be examined and accounted for using fixed or random effects in the models. Characteristics of residents (e.g., age, gender, cognitive function/dementia) and nursing homes (e.g., size, quality, baseline infection rate) will be adjusted. We hypothesize that the ECHO plus effect is heterogeneous and expect stronger intervention effects in subgroups without cognitive dysfunction/dementia as well as those who are younger (HT-1). Subgroup analysis with regard to key participant factors will be performed similarly to examine potential heterogeneity of intervention effects, further tested by interaction analysis (HT-2). If data are sufficient, we plan to explore the heterogeneity of intervention effect on infection rate based on the key participant factors such as age group, gender, dementia, insurance status, and race/ethnicity (HT-3). Outcomes will be assessed after the intervention is initiated (CI-3). Using all measures at 4, 6, 12 and 18 months, we will perform longitudinal analysis to evaluate if the intervention effect changes over time using the same modeling approach but add additional variables for time and time by intervention interaction. Correlations of repeated measures for the same resident will be taken into account in model estimation. Subgroup analysis with regard to key participant factors will be performed similarly to examine potential heterogeneity of intervention effects, further tested by interaction analysis. For cluster-level analyses, the aggregated outcomes (infection, hospitalization) are rates or proportions between 0 and 1 instead of being binary or count variables, we will use Beta regression to model them with a logit link function so that the coefficient can be interpreted as log odds ratio. We will also perform longitudinal analysis for aggregated outcomes based on Beta regression. All statistical tests will be two-sided, with p-values<0.05 considered statistically significant.

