## PROJECT PLAN AND TIMELINE

Upon funding approval, the research team will begin meeting weekly to rapidly prepare the study protocol for stakeholder feedback at the kickoff Advisory Board (AB) meeting. During this meeting, we anticipate receiving feedback and guidance on recruitment strategy, curriculum development, curriculum content, and data collection. Our ECHO infrastructure is set up for rapid launch, with registration, session evaluations, and pre/post-test surveys programmed into REDCap and ready for customization within days for new project launches. We have received promise for an expedited Institutional Review Board (IRB) approval given our institution's prioritization for COVID-19 studies, and the minimum risk proposed. Following IRB approval, recruitment of 200 nursing homes will be completed in collaboration with our state stakeholders. During the next 6 months, we will run weekly ECHO sessions with nursing homes randomized to the intervention. We will continue to meet every other month with stakeholders to guide important study decisions at each research phase. Primary outcomes including COVID-19 infection rate reduction, hospitalizations, and deaths will be collected at 4, 6, 12, and 18 months. Early 6-month outcomes will be discussed with our stakeholders to guide dissemination to both policy and public audiences. At the end of year 1 we will hold an annual in person AB meeting (if allowed) to discuss study updates, challenges, dissemination, and ideas for secondary outcome assessments utilizing the CMS Minimum Data Set. During year 2, the project team will analyze data and implement suggested stakeholder activities for results dissemination and prepare the manuscript of final results.

STEPS AND MILESTONES	Year 1 (Q)				Year 2 (Q)			
Every other month meetings with Stakeholder Advisory Board	X	X	X	X	X	X	X	X
Annual in-person meeting of Investigative Team/Advisory Board				X				X
Subcontract execution	X							
Finalization of study protocol with key stakeholders	X							
IRB Submission and Approval	X							
Study Registration at ClinicalTrials.gov	X							
Begin recruitment of nursing homes	X							
Completion of recruitment of 136 nursing homes		X						
COVID-19 ECHO implementation and delivery	X	X	X	X	X			
Primary outcome assessment: COVID-19 infection rate reduction (4, 6, 12, and 18 months)			X	X	X	X	X	
Secondary outcomes assessment: Flu-like illness, COVID-19 hospitalizations, deaths (4, 6, 12, and 18 months)			X	X	X	X	X	

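### The secondary outcomes are scheduled at baseline, but no model prespecifies adjustment for an outcome's own baseline value; the likely cost is precision, mainly for QOL

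*Combined protocol and SAP*

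**What the plan says.** **Baseline measurement.** The Study Design Overview (section C) states that the patient-centred outcomes, among them "flu-like illness, hospitalizations, deaths, and QOL) will be assessed at baseline (intervention start date), 4, 6, 12, and 18 months". The Outcomes paragraph repeats this schedule. The Effectiveness row of Table 4 gives the sources and times as "National COVID-19 Nursing Home data file and CMS Minimum Data Set (baseline, 4, 6, 12, 18 months". The Project Plan and Timeline differs: its row for three of the secondary outcomes reads "Flu-like illness, COVID-19 hospitalizations, deaths (4, 6, 12, and 18 months", without baseline.

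**Models.** The Sample Size, Power, and Analytic Plan (IR-1) gives one generic approach for all outcomes: generalised linear models of the 6-month outcome, with a link chosen by outcome type and clustering handled by mixed models or GEE. Aggregated outcomes get Beta regression, with no covariate list of its own.

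**Covariates.** One statement serves all outcomes. For residents it names "Characteristics of residents (e.g., age, gender, cognitive function/dementia"; for homes it says "nursing homes (e.g., size, quality, baseline infection rate) will be adjusted". Both lists open with e.g. A separate rule reads: "We will compare the observed confounders between two study arms and adjust them in the analysis if they are not balanced by design".

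**Longitudinal analysis.** "Using all measures at 4, 6, 12 and 18 months, we will perform longitudinal analysis", using the same modelling approach with time and time-by-intervention terms added.

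**The concern.** An outcome's own earlier value is usually among its best predictors. The plan accepts this for infection by naming the baseline infection rate. For the four secondary outcomes it schedules the same kind of measurement and then gives it no stated role, either as a covariate or as a response in the longitudinal model. For QOL, a home's baseline infection rate is no substitute for a resident's own earlier Minimum Data Set (MDS) score.

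Two things are at stake. The first is precision: the first secondary aim hypothesises a significant improvement in QOL, no power is stated for any secondary outcome, and the number of homes is fixed at 126. The second is prespecification: as written, the choice to adjust each secondary outcome for its baseline could be made after the data are seen.

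**Working it through.** **1. Is an own-baseline value named anywhere?**

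| Outcome | Scheduled at baseline (Design Overview, Table 4) | Baseline named as covariate | Baseline named as longitudinal response |
|---|---|---|---|
| COVID-19 infection | yes | yes | no |
| QOL (MDS, resident level) | yes | no | no |
| Flu-like illness (facility file) | yes, but not in timeline row | no | no |
| Hospitalisations (facility file) | yes, but not in timeline row | no | no |
| Deaths (facility file) | yes, but not in timeline row | no | no |

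**2. The plan's only power figure.** It concerns the primary outcome: 80% power for 1% against 0.3%, with 62 and 64 homes and ICC 0.01. With 77.5 residents per home (midpoint of 75-80) and coefficient of variation 0.76:

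- design effect = 1 + ((1 + 0.76²) × 77.5 − 1) × 0.01 = 2.21
- effective sizes = 62 × 77.5 / 2.21 ≈ 2172 and 64 × 77.5 / 2.21 ≈ 2242
- power of a two-sided Wald test of the difference between Poisson rates ≈ 82%

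The figure is reproduced, and this point does not alter it, because baseline infection rate is already a named covariate. There is no corresponding figure for a secondary outcome.

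**3. Illustrative gain for QOL.** Inputs: 77.5 residents per home (from the plan) and ICC 0.05 (assumed for QOL; the plan mentions this value only for infection). The baseline-to-follow-up correlations, rb between home means and rw between residents within a home, are assumed, since the documents give none. Total variance is set to 1.

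- Variance of a home mean without covariates: ICC + (1 − ICC)/77.5 = 0.05 + 0.95/77.5 = 0.0623
- After adjustment for resident score and home mean: ICC(1 − rb²) + (1 − ICC)(1 − rw²)/77.5

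| rb / rw | Adjusted variance | Ratio | Variance reduction | Standard error reduction |
|---|---|---|---|---|
| 0.3 / 0.3 | 0.0623 × 0.91 = 0.0567 | 0.91 | 9% | 5% |
| 0.5 / 0.5 | 0.0623 × 0.75 = 0.0467 | 0.75 | 25% | 13% |
| 0.7 / 0.6 | 0.0255 + 0.0078 = 0.0333 | 0.54 | 46% | 27% |
| 0.8 / 0.7 | 0.0180 + 0.0063 = 0.0243 | 0.39 | 61% | 38% |

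Dividing 126 by the ratio, 126 homes would act like about 138 at r = 0.3 and 168 at r = 0.5. A comparison with 80% power unadjusted would have about 84% and 90% respectively. The ICC matters little: at 0.8/0.7 the ratio is 0.42 for ICC 0.02 and 0.38 for ICC 0.10.

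This calculation ignores unequal home sizes, assumes that every resident has a baseline score, and compares with a model that has no covariates.

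**4. Illustrative gain for the facility counts.** With rare events the correlation between a home's earlier and later rates may be low. Taking 1 − r² as a rough guide, r = 0.1, 0.2 and 0.3 give 0.99, 0.96 and 0.91, a variance reduction of 1%, 4% and 9%.

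**The case against.** The strongest reply is that the plan does not exclude this adjustment. Both covariate lists are illustrative, the longitudinal model inherits the same approach, and the imbalance rule could bring in a baseline QOL score or facility rate. A reader might infer that the baseline data are discarded; the text does not support that. What stands is narrower: adjustment is allowed but not committed to. The imbalance rule depends on the data, gives no precision when the arms look balanced, and does not say that outcome baselines count as confounders.

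A reader might also infer that every secondary confidence interval is wider than it need be. That does not follow. The variance formula is for a linear model of a continuous outcome. In logistic models, adjusting for a prognostic covariate does not in general narrow the interval for the odds ratio, and rare counts may gain little. A resident has no baseline value for death; only the home's earlier rate exists. COVID-19 hospitalisations and deaths follow from infection, and infection status is already a stratification factor and baseline infection rate a named covariate, so some of the relevant information may already be in use.

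The upper figures for QOL are also generous. The correlations are assumed, and age, gender, cognition, size, quality and baseline infection rate are already named, so the added gain is smaller to the extent that these predict QOL.

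Finally, nothing in the documents shows how far back the weekly file holds influenza, respiratory illness or admission fields, and flu-like illness became an outcome only in May 2021. All of these objections stand. They limit the size and reach of the point but do not supply the missing specification.

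**Conclusion.** The plan leaves own-baseline adjustment of the four secondary outcomes unspecified, although it schedules the measurements. This is a gap in precision and prespecification. It is not a source of bias: under randomisation the comparison is valid without the adjustment, and the primary analysis is untouched.

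A material gain is plausible for QOL. The range of 9% to 61% in variance rests wholly on the assumed correlations and on a comparator without covariates, so it bounds the incremental gain loosely from above and cannot be refined from the documents. For flu-like illness, hospitalisations and deaths the gain is likely small. The timeline row that omits baseline is an inconsistency to reconcile. The timeline's row for the primary outcome also lists only months 4 to 18, although a baseline infection rate is a named covariate, so the omission need not mean that baseline is not collected.

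**What to change.** - **QOL, 6-month and longitudinal models:** prespecify adjustment for the resident's baseline MDS score plus the home's baseline mean. For residents without a baseline score, such as those admitted later, use the home mean and an indicator.
- **Flu-like illness, hospitalisations and deaths, in the 6-month, longitudinal and Beta regression models:** prespecify adjustment for the home's own rate over a fixed window before the start, for example 12 weeks, where the weekly file holds the field. State what is done where it does not.
- **Imbalance rule:** state that these covariates enter whether or not the arms look balanced.
- **Timeline:** reconcile the secondary-outcome row with the Study Design Overview and Table 4 on baseline collection.

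The cost is a few sentences in the analysis plan and a check of which fields the weekly file holds before the start date. The baseline measurements are already scheduled.

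### The secondary facility-level Beta regression cannot be fitted when any home has zero cases, and the plan gives no rule for such homes

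*Combined protocol and SAP*

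**What the plan says.** All of this is in section C, under Sample Size, Power, and Analytic Plan (IR-1).

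- The plan separates "individual-level analyses (primary) and cluster-level analyses (secondary"), so the facility-level comparison is pre-specified but not primary.
- For the facility level it reasons that "the aggregated outcomes (infection, hospitalization) are rates or proportions between 0 and 1", and concludes: "we will use Beta regression to model them with a logit link function so that the coefficient can be interpreted as log odds ratio".
- The same model is carried to repeated time points: "We will also perform longitudinal analysis for aggregated outcomes based on Beta regression".
- Count and binary models appear a little earlier, for the main intervention effect, which is to be an odds ratio or an incidence "rate ratio based on logistic, Poisson or negative binomial regressions". They are not offered for the aggregated outcomes.

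Neither this section nor any other names a zero-inflated Beta model, a transformation away from 0, or any other treatment of homes with no events.

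**The concern.** A proportion between 0 and 1 suits Beta regression only if it never equals 0 or 1. A nursing home with no infections in the window has a proportion of exactly 0, and at the rates the plan cites that is an ordinary result. If such homes occur, the stated model gives no estimate, and someone has to choose a repair after seeing the data: shift the zeros, drop the homes, or change the model. The repairs differ in the odds ratio they return and in their false-positive rate. Dropping zero-case homes would also break the intention-to-treat principle that the plan sets for this analysis, and would remove the homes with the best outcome.

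**Working it through.** **1. The plan's own figure.** The inputs come from the power paragraph: 62 and 64 homes; "the average weekly COVID-19 infection rate was 0.1%, average number of residents in nursing homes (cluster size) was around 75-80"; "the coefficient of variation of cluster size was at about 0.76"; "Assuming 1% infection rate in the ECHO arm over the 9 weeks"; 0.3% in ECHO plus; ICC 0.01; two-sided alpha 0.05.

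- Design effect = 1 + [(CV² + 1)m − 1] × ICC = 1 + (1.5776 × 77.5 − 1) × 0.01 = 2.213.
- Effective sizes: 62 × 77.5 / 2.213 ≈ 2,172 and 64 × 77.5 / 2.213 ≈ 2,242.
- SE = √(0.01/2,172 + 0.003/2,242) = 0.00244; z = 0.007/0.00244 = 2.87.
- Power = Φ(2.87 − 1.96) ≈ 82% (81.3% at m = 75, 82.4% at m = 80).

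This agrees with the stated 80%, so the inputs are read as the plan meant them.

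**2. The model at zero.** With mean μ and precision φ, the Beta log-density contains (μφ − 1) log y. At y = 0 this is minus or plus infinity, according to whether μφ is above or below 1. A standard Beta regression (statsmodels) fitted 126 simulated proportions and then refused the same data once a single value was set to 0.

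**3. Expected share of zero-case homes.** For a home of n residents at cumulative rate p:

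- ICC 0: P0 = (1 − p)^n.
- ICC > 0: beta-binomial, P0 = B(a, b + n)/B(a, b), with a = p(1 − ICC)/ICC and b = (1 − p)(1 − ICC)/ICC.
- Share = [62 × mean P0(control) + 64 × mean P0(ECHO plus)]/126.

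The six-month rate is an assumption, because the plan gives none. The value 2.6% is 0.1% per week × 26 weeks; 5%, 10% and 20% are shown beside it. ECHO plus is 20% lower, as the Primary Aim hypothesises. The plan gives only the mean and CV of home size, so three distributions with mean 77.5 and CV 0.76 were used: gamma, lognormal, and a gamma shifted to a floor of 30 residents. Each cell shows the lowest to highest of the three.

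| Control vs ECHO plus | ICC 0 | ICC 0.01 | ICC 0.05 |
|---|---|---|---|
| 2.6% vs 2.08% | 26–29% | 33–36% | 52–54% |
| 5% vs 4% | 10–15% | 14–18% | 29–32% |
| 10% vs 8% | 1.7–5.8% | 2.9–6.9% | 9.5–13% |
| 20% vs 16% | 0.1–1.9% | 0.1–2.2% | 1.1–3.5% |

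Hand check with equal sizes and ICC 0 at 2.6%: 0.974^77.5 = 0.130 and 0.9792^77.5 = 0.196, so (62 × 0.130 + 64 × 0.196)/126 = 16%. Size variation raises the share because small homes are often at zero.

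**4. Chance of at least one zero-case home** = 1 − (1 − P0,control)^62 × (1 − P0,plus)^64.

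- Up to 5%, it is near 1 in every case in the table.
- At 10% vs 8%, the lowest case is the 30-resident floor at ICC 0. Mean P0 is 0.0104 and 0.0229, so 1 − 0.9896^62 × 0.9771^64 = 1 − 0.523 × 0.227 = 88%. At ICC 0.01 the same sizes give 97.5%.
- At 20% vs 16%, it ranges from 7% to 99%.

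**5. What a post hoc rule does.** Trials of 62 and 64 homes were simulated at ICC 0.01 with unadjusted two-arm fits. Four shift rules were compared: (125y + 0.5)/126; (cases + 0.5)/(n + 1); zeros set to 0.001; zeros set to 0.0001.

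- 2.6% vs 2.08%: the true OR is (0.0208/0.9792)/(0.026/0.974) = 0.80. Shift rules give medians of about 0.85–0.90, dropping zero homes about 0.90, and fractional logit 0.79–0.82.
- 10% vs 8%: the true OR is 0.78. Shift rules give 0.76–0.81, so there is little bias.
- No effect, 10% in both arms: rejection at nominal 5% runs from about 4% to 20% depending on the rule, highest when zeros become 0.0001. Fractional logit with HC3-type errors rejected 4.4–6.2% over the null settings run.
- With the 20% reduction, 15–18% of trials at 2.6% and 22–31% at 10% were significant under some but not all of the four rules.

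**The case against.** The strongest reply is that this is an omitted detail in a secondary analysis. A competent analyst would squeeze the zeros or use a zero-inflated Beta model, and the fit would run. In part this stands. A zero-inflated Beta with a marginal effect recovers the true odds ratio (0.81 against 0.80 at 2.6%), so the problem is not inherent in every Beta extension. But several usual repairs exist and they disagree, which is the reason to name one beforehand.

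The simulations have limits. They are unadjusted, whereas the plan adjusts for resident and home characteristics, state and cohort. Setting zeros to 0.0001 is an extreme rule that widens the disagreement between rules. At 2.6% every method compared has low power (about 10–22%), so no rule makes that comparison informative.

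Stronger readings are tempting but not supported:

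- That two-thirds or more of homes will be at zero. The power scenario (1% vs 0.3%) does imply about 66–74% with CV 0.76 and ICC 0–0.01, but it covers nine weeks and is not an analysis time point.
- That zeros are certain at six months. The plan states no six-month rate, and because baseline is the intervention start the window can include Phase 1, when rates may have differed. With 10% in both arms, a 30-resident floor and ICC 0, the chance of a zero-case home is 73%. With equal home sizes it would be lower still, but that contradicts the stated CV.
- That hospitalization has a known share of zeros. The plan gives no hospitalization rate, so none is claimed.

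**Conclusion.** The point holds and should be fixed. Plain Beta regression is undefined for a zero-case home, and the plan has no rule for one. At cumulative control rates from 2.6% to 10%, with the plan's home numbers, mean size and size CV, ICC 0–0.05 and a 20% reduction, between about 2% and 54% of homes are expected at zero. At least one is nearly certain up to 5% and about 88% or more likely at 10%. Near 20% there may be none, and the stated model could then run.

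The harm is real but limited. At low rates, shifting zeros pulls the estimate toward no effect. At 10% bias is small, but the false-positive rate depends on the rule. These sizes rest on assumed six-month rates, assumed size distributions and unadjusted fits. A reader might infer that the trial's main result is at risk. It is not: the primary individual-level analysis uses other models and is unaffected.

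**What to change.** In Sample Size, Power, and Analytic Plan (IR-1), replace Beta regression for the aggregated infection and hospitalization outcomes with fractional logit: a quasi-binomial model with logit link on facility proportions and small-sample-corrected robust standard errors. Use facility-clustered GEE for the repeated periods. This admits zeros and keeps the log odds ratio that the plan gives as its reason for choosing Beta regression.

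If a rate ratio is preferred, negative binomial regression on facility case counts with a log resident-weeks offset is acceptable. Name one of the two before outcome data are analysed.

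The cost is two sentences and standard software; the public file already supplies aggregate facility cases. Fractional logit has somewhat less power than the count model (about 51–60% against 67% at 10% vs 8%, ICC 0.01; 18–19% against 21–22% at 2.6%). The count model changes the effect measure, gives larger homes more weight, and overlaps with models already listed, so it is less independent as a secondary check.
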